6.5. Medications

6.5.1. Prior Medications

All medications will be classified using the Anatomical Therapeutic Chemical (ATC) classification codes and preferred drug names from the World Health Organization Drug Dictionary ((WHO-DD, version from June 2016)). Medications with a stop date before the first date of study drug dosing in this study will be considered prior medications. Summaries of PD prior medications will be presented in tabular form using the ATC Level 4 and preferred term. Other prior medications will be presented in tabular form using the ATC Level 1, ATC Level 2, and Preferred Term (PT). Frequencies and percentages of patients receiving medications will be presented by treatment regimen and overall. The tables will be sorted by overall descending frequency of ATC Level(s) and then, within an ATC Level, by overall descending frequency of PT.

- For derivation and dates imputation see section 6.5.2 in concomitant medication

6.5.2. Concomitant Therapy or Medication

Medications with start date or stop date on or after the first date of study drug dosing or ongoing at study completion will be considered concomitant medications.

Separate summaries of concomitant PD treatment medications (medications which start with ATC code N04) will be presented in tabular form using the ATC Level 4 and preferred term. Other concomitant medications will be presented in tabular form using the ATC Level 1, ATC Level 2, and Preferred Term (PT). Frequencies and percentages of patients receiving medications will be presented by treatment group and overall. The tables will be sorted by overall descending frequency of ATC Level(s) and then, within an ATC Level, by overall descending frequency of PT.

If the medication start date is incomplete, then it will be imputed as follows for the purpose of determining concomitant use:

- If the start date is completely missing, the start date will be equal to the first dose date. However, if the stop date is not missing and is before the first dose date, then the stop date will be used instead.
- If the start day is missing, the first day of the month will be used.
- If the start day and month are missing, then the first day of the first month (January) will be used.

If the medication stop date is partial, then it will be imputed as follows for the purpose of determining concomitant use:

- If the stop date is completely missing and the medication is not ongoing, the stop date will be equal to the last dose date or date of completion/withdrawal, whichever is the latest.
- If the stop day is missing, the last day of the month will be used.
- If the stop day and month are missing, then the last day of the last month (December) will be used.

The summary of prior and concomitant medications will be done for the Safety set broken down by treatment group.

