For both cohorts, if required, subjects and their study partners will be trained and assisted at their homes during the first week of treatment by the Home Nursing Service on the correct administration technique. One mandatory home visit will be performed during the first week, preferably on Day 3. Throughout the 12-month treatment period the Home Nursing Service will visit the subjects at their homes on a monthly basis.

For both cohorts, during the treatment period (up to Month 102), a helpline will be available for subjects/study partners to call at any time should they encounter any difficulties with the pump system.

The planned treatment duration for all regimens is 12 months with in-clinic visits at Week 1, Month 1, Month 2, Month 3, Month 4, Month 6, Month 9 and Month 12.

Subjects will be allowed to continue with study treatment for an optional treatment extension period of 24 more months in which clinic visits will be performed every 3 months to assess subject safety. Subjects will be offered another optional long-term treatment extension period up to Month 102. During this long-term extension period, clinic visits will continue to be performed every 3 months to assess subject long-term safety.

Safety follow-up visits will be performed 1, 2 and 3 months after the last SC administration of the study drug.

This will be the third study to assess the administration of the ND0612 solution using different dosing regimens in a home setting, with the focus of the current study being on the safety of long-term home administration. Additionally, the study will explore the need for dose adjustments e.g., up and down titrations of the study drug and/or a need for additional oral anti-PD treatment.

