- Assessment of Clinical Global Impression of disease severity by investigator or designee using CGI-S (see Section 10.2.1.3 and Appendix 17.10.1)
- Cohort 2: Collection of "ON/OFF" home diary. Entries will be reviewed for completeness and accuracy and data recorded in the eCRF.
- Cohort 1: Dispense "ON/OFF" home diary for entry of baseline motor assessment that will be performed on Days 2 and 3
- Dispense new "ON/OFF" home diary (see Section 10.2.1.1 and Appendix 17.12) Pump diary (see Section 10.1.11 and Appendix 17.13)
- Provide training on Pump diary use
- Administration of standard LD/DDI therapy throughout the day until infusion is started
- SC infusion will be started at the clinic at a convenient time on Day 1 for subjects on all regimens. The SC infusion will be applied by subject or study partner with the supervision of the study site staff. Infusion site assessments will be performed and infusion site reactions will be reported as AESI (see Section 10.1.3)
- Recording of AEs including SAEs and AESIs
- Dispensing of study medication and clinical supplies for 1 month
- Subjects will leave the clinic with their infusion pump attached, programmed according to the assigned regimen, and locked, and a supply of infusion sets and syringes sufficient for 1 month

• On the Baseline visit only, additional supply of infusion sets & syringes for 30 extra days will be dispensed to serve as back up for the 12-month treatment period

Subjects and study partners will be instructed to continue administration of the study drug at their homes according to their assigned regimen, and to contact the helpline if they need assistance. Home visits by the Home Nursing Service may be performed as needed during the first 7 days of treatment to provide additional training on the use of the infusion pump system including the application of infusion sites and the changing of the syringes and infusion sets. One home visit during the first week of study treatment is mandatory and should be performed preferably on Day 3.

9.2.2 Day 2

All subjects in Cohort 2 will return to the clinic on Day 2. Subjects in Cohort 1 who perform the completion visit of ND0612H-006 on the same day as the baseline visit of ND0612H-012 do not need to perform this visit. The subjects will arrive to the site after they have administered the study drug at a new infusion site.

The following procedures will be performed on Day 2:

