9.2.4 Safety Follow-up Visit 1 (1 Month after Last Study Treatment)

Subjects will return to the clinic 1 month after the completion of the last study treatment for a safety follow-up visit. This will be at Month 13 for subjects who choose not to continue treatment in the optional treatment extension period, or Month 37 for subjects who continue treatment in the treatment extension period, or Month 103 for subjects who continue treatment in the long-term treatment extension period. In case of early termination, this visit is to be scheduled about 1 month after the Early termination visit. The following procedures are scheduled for this visit:

- Concomitant medication review (including anti-PD medication).
- Urine pregnancy test for female subjects of childbearing potential

- Vital signs (including supine [after resting for at least 5 min] and standing BP, pulse rate, and body temperature
- Body weight
- 12-lead ECG recording (single)
- Safety laboratory tests, including blood chemistry, hematology, and dipstick urinalysis (see Section 10.1.2 for details) if deemed necessary by the investigator to follow-up on earlier clinically significant findings
- Physical and neurological examination
- Assessment of suicidality using C-SSRS (see Section 10.1.8 and Appendix 17.3)
- Assessment of impulsive-compulsive disorders in PD using the QUIP-RS (see Section 10.1.10 and Appendix 17.4)
- Assessment of excessive daytime sleepiness using ESS (see Section 10.1.9 and Appendix 17.5)
- Infusion site assessments will be performed and infusion site reactions will be reported as AESI (see Section 10.1.3)
- Recording of AEs (including SAEs and AESIs)

For safety follow-up visits after the optional extension period and the optional long-term extension period, 12-lead ECG and optional safety laboratory test data (blood chemistry, hematology, and dipstick urinalysis) will be analysed locally (i.e., not at a central lab/by central reader).

9.2.5 Safety Follow-up Visits 2 and 3 (2 and 3 Months after Last Study Treatment)

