9.2.8 Early Termination Visit

Subjects who decide not to continue with the study procedures or who are withdrawn from the study should complete an early termination visit.

Procedures at the early termination visit are the same as mentioned in Section 9.2.3 for the Month 12 visit, with the addition of a neurological and a physical examination. Subjects will be prescribed an appropriate commercial LD/DDI dose as determined by the investigator and will return the infusion pump system to the site.

Early termination visits should also be performed for any subject who prematurely discontinues from the optional treatment extension period and the optional long-term extension period. For early termination visits during the extension periods, safety laboratory tests (blood chemistry, hematology, and dipstick urinalysis) and 12-lead ECG recordings should be done at the investigator's discretion and associated data will be analysed locally (i.e., not at a central lab/by a central reader).

Reasons for withdrawal of the subject before completion of the study must be stated in the eCRF and in the site source documentation for all study subjects who were enrolled in the study. The sponsor should be informed of all subjects who are withdrawn due to AEs.

An in-person safety follow-up visit should take place 1, 2 and 3 months after the actual discontinuation of the study drug. See Section 9.2.4 and Section 9.2.5 for procedures at the safety follow-up visits.

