7.3.4. Adverse Events

Adverse events will be coded using MedDRA. Adverse events will be grouped by SOC and preferred term (PT). Only treatment emergent adverse events will be summarized. Treatment Emergent Adverse Events (TEAEs) are defined as all AEs that start (or worsen) on or after the start of first study drug administration in this study and before the start of the optional treatment extension. It is assumed that AEs that started in study ND0612H-006 will not be recorded on the case report form of the present study (unless the event in question worsened during the present study), as these events will not be TEAEs in the present study. For patients who do not participate in the optional treatment extension, events that start >28 days after the last dose of study medication will not be defined as TEAEs. The summary tables will present the frequency and percentage of total subjects and number of events, by SOC and by PT.

For tables of incidence of AEs, subjects who experience the same AE (in terms of the MedDRA PT) more than once will only be counted once for that event in the number of subjects but all occurrences of the same event will be counted in the number of events.

Events with a missing start time, but with a start date equal to the date of first dose of study treatment after baseline will be considered treatment-emergent. If the AE start date is incomplete, it will be imputed as follows for the purpose of determining TEAE:

- If the start date is completely missing, the start date will be equal to the date of the first dose of study treatment. However, if the stop date is not missing and is before the date of the first dose of study treatment, then the stop date will be used instead.
- If the start day is missing, but the month and year are not missing and are equal to the month and year of the first study dose, then this event will be considered as TEAE.
- If the start day and month are missing, then the first day of the first month (January) will be used.

The original date and time will be shown on all listings of AEs. Listings will be provided for all AEs, serious AEs, AEs leading to study treatment discontinuation, AEs leading to dose adjustment/temporary withdrawal and deaths.

The following summaries will be provided:

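### The concomitant-medication window has no end at the last ND0612 dose or at the start of the extension, so drugs begun afterwards enter the 12-month concomitant tables

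*SAP*

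**What the plan says.** SAP 6.5.2 takes as concomitant "Medications with start date or stop date on or after the first date of study drug dosing or ongoing at study completion". SAP 6.5.1 supplies the other half: "Medications with a stop date before the first date of study drug dosing in this study will be considered prior medications". The first dosing date is the only reference point in either rule. The classification feeds two sets of tables on the Safety Set by treatment group: anti-PD drugs (ATC code N04) by ATC Level 4 and preferred term, and all other drugs by ATC Levels 1 and 2 and preferred term.

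The protocol creates the records that test the rule:

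- **End of treatment.** Section 9.2.3 has LD/DDI prescribed at Month 12 when the pump is returned. Section 9.2.8 says of early termination: "Subjects will be prescribed an appropriate commercial LD/DDI dose as determined by the investigator".
- **After treatment.** Section 9.2.4 reviews medication, anti-PD drugs included, one month after the last study treatment. Section 9.2.9 records it at any unscheduled visit.
- **Extension.** Sections 9.2.6 and 9.2.7 review medication at every extension visit.
- **Dataset.** Section 11.1.6 adds to the 12-month data whatever safety follow-up data exist at database lock.

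Protocol 11.1.3.2 lists prior and concomitant medications among the secondary safety measures for the 12-month treatment period.

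**The concern.** A concomitant-medication table is read as a list of what subjects took alongside the study drug. Here it would mix add-on therapy taken during infusion with replacement therapy taken because infusion had ended. That matters more than usual in this trial, because Protocol 6.5 says the study will explore "a need for additional oral anti-PD treatment". The SAP's efficacy sections (3.2.3 and 8.2) define no analysis of change in oral LD/DDI dose, although the protocol lists it as an endpoint. That omission is a separate matter, but it leaves the N04 table as the main SAP summary of oral anti-PD use after baseline.

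Only subjects who have stopped ND0612 can contribute a post-treatment entry. If one regimen loses more subjects, its table has more room for such entries, and a difference in discontinuation could look like a difference in need for add-on drugs. Apomorphine gives a hypothetical example. Protocol 8.4.9.1 bars it only during ND0612 treatment, yet a course begun afterwards would be tabulated as concomitant and could be mistaken for a prohibited medication.

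**Working it through.** The plan states no figure on this point. The check applies the rule to dated records.

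**Inputs.** Illustrative subject: first dose F = Day 1, last dose in the 12-month period L = Day 365. Safety Follow-up 1 falls four weeks after the last treatment (Protocol 8.1.2, notes to the schedule): 365 + 28 = Day 393.

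**SAP rule.** Prior if stop < F. Concomitant if start ≥ F, or stop ≥ F, or ongoing at study completion.

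**Closed rule.** As above, and also start ≤ L and start before the extension begins.

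| Record | Start | Stop | SAP rule | Closed rule |
|---|---|---|---|---|
| A. Drug stopped before dosing | before Day 1 | Day -1 | prior | prior |
| B. Oral LD/DDI last taken on Day 1 | before Day 1 | Day 1 | concomitant (1 ≥ 1) | concomitant |
| C. Adjunct oral LD/DDI, ongoing | before Day 1 | none | concomitant | concomitant |
| D. Drug used on treatment | Day 50 | Day 60 | concomitant | concomitant |
| E. LD/DDI begun the day after the last dose | Day 366 | none | concomitant (366 ≥ 1) | post-treatment (366 > 365) |
| F. Other drug begun 10 days after the last dose | Day 375 | Day 385 | concomitant (375 ≥ 1) | post-treatment (375 > 365) |
| G. Drug begun in the extension | Day 450 | none | concomitant (450 ≥ 1) | outside the 12-month tables (450 > 365) |

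E and F both fall before Day 393, so the scheduled review captures them. Neither was taken with ND0612. G was taken with ND0612, but outside the period that the 12-month tables describe.

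**Is there an end date elsewhere?**

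- Protocol 11.1 limits the primary-objective analyses to data up to the Month 12 visit. That does not stop the window at the last dose for an early discontinuer, and Protocol 11.1.6 adds follow-up data.
- SAP 1.1 says the document covers the main study only, but does not say which medication records that removes. SAP 3.5.2 holds the analyses until the last patient completes 12 months, when earlier enrollees may already have extension records.
- SAP 7.3.4 closes the adverse-event window at the start of the extension. For subjects who do not extend, "events that start >28 days after the last dose of study medication will not be defined as TEAEs". SAP 6.5.2 has no counterpart to either limit.

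**The case against.** Three arguments against the point carry weight.

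**The window is bounded in practice.** After Safety Follow-up 1, the remaining follow-up visits are limited to pregnancy tests and infusion-site assessment (Protocol 9.2.5). For subjects who do not extend, scheduled capture therefore ends close to the 28-day adverse-event limit. This stands as a limit on how much is miscounted. But the month that is captured is the one in which replacement therapy starts, and the argument does not cover extension records.

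**Many rows will barely move.** Patients are counted once per preferred term, so restarting a drug already recorded on treatment adds nobody. Oral LD/DDI is expected to be tapered from an existing dose, and Regimen 3 has a mandatory morning dose. This stands: the distortion falls mainly on drugs not used during infusion.

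**Cutting at the last dose has a price.** Drugs given for treatment-emergent events in the following 28 days leave the concomitant table. This also stands, and they must remain visible in a separate table.

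A reader might also infer that the Day 1 boundary is wrong, because a subject who stops oral LD/DDI that day is still counted. The documents do not support changing it. The inclusive boundary is a usual date-level convention and the exact complement of SAP 6.5.1. The rule uses dates, not clock times, and Protocol 8.1.1 lets a further oral dose be considered after the pump starts, so a Day 1 stop may be true co-use. For Cohort 1 subjects rolling over directly, it may also follow ND0612 exposure in study ND0612H-006.

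**Conclusion.** The point holds for the open upper end of the window. Followed exactly, SAP 6.5.2 reports drugs first started after the last ND0612 dose as taken with it, and brings drugs first started in the extension into the 12-month tables. This rests on the written rule and the protocol's own data collection, not on an assumed rate.

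The effect is confined to descriptive tables. No primary endpoint, model or test uses this classification, and all data are listed by patient (SAP 5.1). Its size cannot be computed, because the documents give neither the number of subjects who stop nor the number who then start a new drug. A count of affected subjects would rest wholly on assumed rates.

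A reader might also infer that the rule forces oral levodopa use in Cohort 2, Regimen 1 to 100%, and that closing the window would reveal who managed without it. The documents do not support that. A high figure there mostly reflects an any-use table in a trial where oral LD/DDI is continued and then tapered (Protocol 8.4.1). Closing the upper end leaves those subjects concomitant.

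**What to change.** In SAP 6.5.2, keep the inclusive first-day boundary and add two conditions for a concomitant drug: its start date is on or before the last ND0612 dose in the 12-month period, and before the start of the optional extension. Leave SAP 6.5.1 unchanged. For subjects who stop ND0612, tabulate drugs started after the last dose separately as post-treatment medication. Leave drugs started in the extension to the separate extension SAP.

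Two consequences should be stated in the text. A drug started on the date of the last dose stays concomitant, because dates alone cannot order the two; this mirrors the Day 1 convention. A drug with a missing start day is imputed to the first of the month (SAP 6.5.2), so one begun in the month of the last dose can also stay concomitant.

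The cost is one clause and one small table, using dates already collected. The downside is that drugs given for treatment-emergent events in the 28 days after the last dose move to the new table; a footnote should say so.

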6.6. Electrocardiography

Electrocardiogram findings (normal, abnormal, and missing) at baseline will be summarized using descriptive statistics.

6.7. Physical Examinations

Physical examinations will be summarized at screening and Baseline. An abnormality at screening should be collected as a part of medical history.

6.8. Protocol Deviations

The important protocol deviations in the study will be listed.

7. SAFETY

7.1. General

All safety summaries will be produced for the Safety Set. In general, all safety endpoints will be summarized using either summary statistics or frequency tabulations, as applicable to the type of data.

Cohort 1 and Cohort 2 will be analyzed jointly and separately. This analysis will include the following treatment groups:

- Cohort 1, Regimen 1
- Cohort 2, Regimen 1
- Cohort 2, Regimen 3
- Cohort 2, Total
- Cohort 1+2 combined, Regimen 1
- Cohort 1+2 combined, Total

An additional safety analysis will be conducted by excluding the safety data from the patients who received Regimen 2 during the period when these patients received Regimen 2 (i.e. by excluding the data captured after the first dose of Regimen 2 until the switch to Regimen 1). This additional analysis will be done at least for extent of exposure, tolerability and selected adverse event summaries. The safety data from the optional treatment extension will be combined with the safety data of the main study and will be analyzed similarly as defined below using the Follow-up Safety Set. These analyses will be defined in more detail in the separate SAP of the optional treatment extension period.

7.2. Study Drug Administration

Duration of treatment (days treated) is the number of days on treatment based on the first and last days of treatment with the study drug (last day of study drug – first day of study drug + 1).

The following information will be summarized by treatment regimen and overall.

- The number of patients exposed to study treatment
- Mean Duration of exposure (days)

- Total exposure to study treatment, expressed as person years (sum of exposure to study treatment over all patients, classified by treatment regimen)
- Number of patients who reduced ND0612 dose and the mean reduction from baseline to each visit

7.3. Primary Analyses

7.3.1. Adverse Events of Special Interest (AESI)

Adverse Events of Special Interest (AESI) will include the following:

- Injection Site Reactions (ISR's)
- Cases of Hypersensitivity (e.g. diffuse skin rash, anaphylaxis and angioedema).
- Polyneuropathy (EMG-ENG & Vit B: 6 and 12, Folate and Homocysteine)

